## TITLE COLLAPSIBLE PESSARY FEASIBILITY TRIAL STATISTICAL ANALYSIS PLAN

**11.0 PAIN ASSOCIATED WITH INSERTION & REMOVAL (SECONDARY)**

- 11.1 Endpoint
  - 11.1.1 Pain associated with study pessary insertion compared to current pessary
  - 11.1.2 Pain associated with study pessary removal compared to current pessary
- 11.2 Data collection method
  - 11.2.1 Pain will be assessed using a VAS with a 10 cm linear continuum in which 0 represents no pain and 10 represents worst pain.
- 11.3 Analysis group
  - 11.3.1 At most, for each subject two VAS pain scores will be collected for each of insertion of current pessary, insertion of the study pessary, removal of the current pessary, removal of the study pessary. Subject's VAS pain scores will be included in the comparative analysis group if the subject has at least 1 data point for both the study pessary and their current pessary and in the non-comparative analysis group if they have at least 1 data point for the study pessary.
- 11.4 Data analysis plan
  - 11.4.1 For each subject, average pain scores for the current pessary and study pessary will be calculated.
  - 11.4.2 For each subject, a difference (current pessary – study pessary) in average pain scores will be calculated.
- 11.5 Reportable outcomes
  - 11.5.1 Average and standard deviation of the pain of current and study pessary insertion and removal will be reported.
  - 11.5.2 We will use a two-tailed t-test to test the null hypothesis that the mean difference score between baseline (current pessary) and study pessary for pain during insertion is zero. This test is equivalent to a matched samples t-test. The p-value will be reported.
  - 11.5.3 We will use a two-tailed t-test to test the null hypothesis that the mean difference score between baseline (current pessary) and study pessary for pain during removal is zero. The p-value will be reported.

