	Pelvic Floor Impact Questionnaire (PFIQ- 7)	Between enrollment and the end of washout	Pelvic Floor Impact Questionnaire -7 is a health-related quality of life instrument, designed to assess the life impact of pelvic floor symptoms in women with pelvic floor disorders. The PFIQ-7 has a parallel structure to the PFDI with 3 Scales: CRAIQ, POPIQ and IIQ.
Secondary	Pelvic Organ Prolapse/Urinary Incontinence Sexual	the end of washout	A validated evaluation tool which can be used clinically as well as in research for assessment of female

DEIA	DOCUMENT NUMBER	CP-002-01	r 03
KEIA		PAGE	8 of 23

TITLE COLLAPSIBLE PESSARY FEASIBILITY TRIAL PROTOCOL

	Questionnaire, IUGA- Revised (PISQ-IR)	[Week 0-4] and post treatment [Week 16]	sexual function (FSF) in women with female pelvic floor disorders.
	Objective assessment of the pessary's ability to support the prolapse	At enrollment [Week 0], during treatment [Week 3-5], and during treatment [Week 16]	POP-Q points Ba and Bp (measurements of prolapse) will be measured during physical exam, with the pessary in situ.
Secondary	Global assessment of study pessary satisfaction compared to current pessary	For current pessary at the end of washout period [Week 3-5]; For study pessary post treatment [Week 16]	Satisfaction will be assessed using a Visual Analog Scale (VAS) with a 10 cm linear continuum in which 0 represents no satisfaction and 10 represents complete satisfaction.
Secondary	Pain associated with study pessary insertion compared to current pessary	During treatment [Week 3-5], during treatment [Week 5-7], and post treatment [Week 16]	Pain will be assessed using a Visual Analog Scale (VAS) with a 10cm linear continuum in which 0 represents no pain and 10 represents worst pain.
	Pain associated with study pessary removal compared to current pessary	During treatment [Week 3-5], during treatment [Week 5-7], and post treatment [Week 16]	Pain will be assessed using a Visual Analog Scale (VAS) with a 10cm linear continuum in which 0 represents no pain and 10 represents worst pain.
Other	Proportion of subjects successfully fit with the study pessary	Post treatment [Week 16]	Proportion of subjects who were successfully fit with the study pessary.
Other	Change in frequency of pessary removal for self-managers	Post treatment [Week 16]	The monthly frequency of pessary self-removal during the washout period will be compared against monthly frequency of self-removal in the treatment phase.

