Visit 1 [research purposes] will aim to be scheduled between 3 and 5 weeks from Visit 0 (the conclusion of the washout period). Demographic and historical data will be extracted from the Electronic Medical Record (EMR) if not completed at Visit 0 and supplemented by the subject as needed. Global subject satisfaction of the current pessary will be assessed using a Visual Analog Scale (VAS) with a 10 cm linear continuum in which 0 represents no satisfaction and 10 represents complete satisfaction. As in Visit 0, the current pessary will be observed in situ for the presence of rotation and its ability to support prolapse by measuring the distance of the most dependent compartment of the subject's prolapse to the hymen (points Ba and Bp), as well as the distance from the leading edge of the current pessary to the hymen. The current pessary will be removed, washed, placed in a sealed bag, labeled and either stored or given to the subject for them to return with at their final visit. The physical exam will be repeated as in Visit 0, and the presence of perineal disruption associated current pessary removal will be noted. The appropriate study pessary size for the subject based on the provided mapping from the subject's current pessary and practitioner's expertise will be selected at random from the inventory of study pessaries, removed from its sealed bag, and the study pessary's serial number (labeled on the bag) will be recorded. The subject will be fit with the study pessary. If a study pessary cannot be fit, and the patient is willing, they can be fit with a different sized pessary at Visit 1 or can remain in the study and return for a second attempt to be fit with a study pessary at Visit 2. A VAS will be used to assess the perceived discomfort with removal of the current pessary and, separately, with insertion of the study pessary. For self-managers, ease of current pessary removal and reinsertion will be noted using a VAS and teaching will be provided on the proper technique to insert and remove the study pessary.

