Visit 2 [research purposes] has the option to be omitted, at the discretion of the practitioner and the subject, and will be aimed to be scheduled within 1-3 weeks of Visit 1. The subject will receive a phone call just prior to this visit. The subject will be asked about pessary use and adverse events. If the subject is doing well without any study related concerns, the practitioner and subject can decide if this visit can be omitted. The purpose of this visit is to minimize unforeseeable risks associated with use of the study pessary and/or to refit a subject with a study pessary if the original one was expelled or could not be inserted during Visit 1. If conducted in person, physical exam will be performed to assess for vaginal pathology (ecchymoses, abrasions, superficial cuts, erosions, granulation tissue or bleeding) or urinary retention related to the study pessary, and all adverse events will be recorded. The study pessary will be observed in situ for the presence of rotation and its ability to support prolapse by measuring the distance of the most dependent compartment of the subject's prolapse to the hymen, as well as the distance from the leading edge of the study pessary to the hymen. Those subjects who

were not successfully fit with a study pessary in their first visit would be fit with a new study pessary.

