Visit 3 [research purposes] will occur at the conclusion of the 3-month (from Visit 1) treatment phase - a typical length of time between routine visits for patients who choose long term pessary management of their prolapse. It can be scheduled in a window between 11 and 13 weeks from Visit 1. When the subject returns for Visit 3, a physical exam will be repeated, as in previous visits, for comparative data. The study pessary will be observed in situ for the presence of rotation and its ability to support prolapse by measuring the distance of the most dependent compartment of the subject's prolapse to the hymen (Points Ba and Bp), as well as the distance from the leading edge of the study pessary to the hymen. A VAS will be used to assess discomfort with removal of the study pessary, discomfort with reinsertion of their current pessary, and their global satisfaction of the study pessary. The subject will have been instructed to return with their current pessary which was removed in Visit 1. If the subject's current pessary is not brought to the visit, they will be given a new pessary of the size and style of their current pessary. Each subject will complete the PFDI-20, PFIQ-7, and PISQ-R for a post treatment comparison. For self-managers, other data collected will include frequency of removal and a VAS for ease of study pessary insertion and removal.

Additional Visits: Subjects will be seen as necessary and adverse events will be managed according to standard of care. If the study pessary falls out after Visit 1, the subject may be seen at their convenience for reinsertion or resizing. If a study pessary cannot be fit and retained, the subject will be withdrawn from the study and their current pessary will be placed. If the subject's current pessary is not brought to the visit, they will be given a new pessary of the size and style of their current pessary.

Special Circumstances: If a subject dies between Visit 1 and Visit 3, an attempt will be made to contact the coroner to retrieve the study pessary. If the study pessary cannot be retrieved, a copy of the death certificate will be obtained.

The study pessary is the only device that will be used in this trial. There will be no placebo devices placed. The study pessary is not cleared by the FDA, and a rationale is provided for a non-significant risk device claim in the attached documents.

Data Collected

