13.0 Withdrawal of Subjects

Reasons for a subject to be withdrawn from the research study include:

- The subject is found to have a condition that does not allow participation in the research, such as a finding upon physical examination that excludes them from the study.
- The subject no longer tolerates their current pessary during the washout period or needs a different size or type of pessary during the washout period.
- The subject is not able to be fit with a study pessary at the conclusion of Visit 2, or the study pessary is repeatedly expelled.
- The study pessary causes discomfort or adverse reaction for which continued use is contraindicated.
- The subject has a reaction that requires immediate removal of the study pessary.
- The subject may withdraw themselves at any point for unforeseen circumstances.

DELA	DOCUMENT NUMBER	CP-002-01	r 03	
REIA		PAGE 16 OF 23		
TITLE COLLAPSIBLE PESSARY FEASIBILITY TRIAL PROTOCOL				

If a subject is removed from the study, already collected data may not be removed from the study database and will be handled with the same protocol as research data. The subject will receive the usual ongoing care for their pessary.

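### The plan does not require a removal-pain score when the study pessary is taken out at a withdrawal or unscheduled visit, so the removal-pain comparison may under-represent women who withdrew for discomfort

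*SAP*

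**What the plan says.** **When removal pain is scored.** The endpoint table in Protocol 4.0 gives the times for removal pain as "During treatment [Week 3-5], during treatment [Week 5-7], and post treatment [Week 16". All three are scheduled visits. The visit descriptions in Protocol 6.0 are narrower:

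- Visit 1: "A VAS will be used to assess the perceived discomfort with removal of the current pessary and, separately, with insertion of the study pessary". A woman who reaches fitting should therefore have a current-pessary removal score. Visit 1 has no routine study-pessary removal score.
- Visit 2: this visit "has the option to be omitted, at the discretion of the practitioner and the subject", and its text names no VAS.
- Visit 3: "A VAS will be used to assess discomfort with removal of the study pessary, discomfort with reinsertion of their current pessary". This is the only visit description that scores removal of the study pessary.

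**What happens on early exit.** Under Additional Visits, Protocol 6.0 states: "If a study pessary cannot be fit and retained, the subject will be withdrawn from the study and their current pessary will be placed". Protocol 13.0 lists among the withdrawal reasons: "The study pessary causes discomfort or adverse reaction for which continued use is contraindicated". Neither place mentions a VAS.

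**How the scores are analysed.** SAP 11.3.1 allows up to two study-pessary removal scores per woman without naming the visits. Its inclusion rule reads: "included in the comparative analysis group if the subject has at least 1 data point for both the study pessary and their current pessary". SAP 11.5.3 is a two-tailed t-test of the mean paired difference. Section 11 contains no missing-data rule, no sensitivity analysis and no count of women left out.

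**The concern.** The two sides of the pair are collected under different conditions. The current-pessary score comes before the study pessary is fitted. The only study-pessary score that the visit text requires comes about three months later, from women still in the study. A woman who has the pessary taken out early because it hurts undergoes a removal, but the protocol does not say that it is scored. If it is not, and she has no other removal score, she leaves the analysis.

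Missingness can then depend on discomfort with the device, which is plausibly related to pain at removal. Protocol 3.0 presents easier and more comfortable removal as a purpose of the design, so this comparison bears on a main device claim. If unscored women had worse removals, the mean in the scored women flatters the study pessary.

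Elsewhere the SAP does address early exit. Section 6.3.1 assigns a value to PFDI-20 dropouts, and section 10.3.1 accepts satisfaction scores given before a woman leaves. Section 11 has neither provision.

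**Working it through.** **Plan's own figures.** The documents give no SD, effect size or power for removal pain, so there is nothing to reproduce. The one stated power (0.80) concerns the PFDI-20 and does not bear on this point. The usable inputs are the enrolment figures in Protocol 6.0: at least 50 enrolled and at least 40 completing, an allowance of 1 - 40/50 = 20%, or 10 women, for all causes together.

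**Assumptions (not in the documents).**

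- k = unscored women who withdrew for discomfort, at most 10.
- d = how much worse their difference (current minus study) is than that of scored women: 1 to 3 cm.
- SD of the paired difference: 2 to 3 cm.
- 40 women scored, and a two-sided test at 0.05. SAP 11.5.3 states no alpha.

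**Shift.** If the true mean difference over all 40 + k women is zero, the scored women have mean

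shift = d × k / (40 + k), positive values favouring the study pessary.

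For k = 3: 1 × 3/43 = 0.07 cm and 3 × 3/43 = 0.21 cm. For k = 10: 1 × 10/50 = 0.20 cm and 3 × 10/50 = 0.60 cm.

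**Chance of a significant result favouring the study pessary.** This is the upper tail of a noncentral t with 39 degrees of freedom beyond 2.023, with noncentrality shift × √40 / SD. For k = 3, d = 3, SD = 2 the noncentrality is 0.209 × 6.325 / 2 = 0.66 and the probability is 9.4%. The nominal value is 2.5%.

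| k | Shift, d = 1 to 3 cm | Lowest (d = 1, SD 3) | Highest (d = 3, SD 2) |
|---|---|---|---|
| 1 | 0.02 to 0.07 cm | 2.8% | 4.1% |
| 3 | 0.07 to 0.21 cm | 3.5% | 9.4% |
| 10 | 0.20 to 0.60 cm | 6.1% | 45.7% |

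A simulation of the last cell gave 45%.

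**What scoring at withdrawal would recover.** If r of 10 such women are scored, the remaining shift is d × (10/50 - r/(40 + r)). With d = 3: r = 0 gives 0.60 cm, r = 5 gives 3 × (0.200 - 0.111) = 0.27 cm, and r = 10 gives 0.

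**The case against.** A reader might infer that every woman who withdraws because of pain goes unscored, and that the comparison therefore describes only women who tolerated the pessary. The documents do not support that, for these reasons:

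- They are silent on scoring at withdrawal; they do not rule it out. The data collection form (CP-002-03), which may settle it, is not among the documents reviewed.
- SAP 11.3.1 requires one score, not completion of Visit 3. It does not exclude withdrawals or failures to fit, whereas 9.3.2 does exclude failures to fit. A score taken at withdrawal or during refitting would count.
- Women with early problems are more likely to be seen in person at Visit 2, because the condition for skipping it is: "If the subject is doing well without any study related concerns, the practitioner and subject can decide if this visit can be omitted". If removal is scored there, as the endpoint table implies, a woman who later withdraws stays in.
- Not every loss is a painful removal. Expelled or never-fitted pessaries may leave nothing for a practitioner to remove, some women leave during washout, and discomfort in wear is not the same as pain at removal.
- Intolerance is visible elsewhere. Discomfort at insertion or removal is a listed adverse event, analysed in all women who complete Visit 0, and some discomfort withdrawals may be counted as failures to fit under SAP 12.3.2.

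A reader might also take the 46% cell as the expected error rate. It needs all 10 losses to be unscored discomfort withdrawals, each 3 cm worse, with an SD of 2 cm. The 10 are counted from enrolment at Visit 0 and cover every cause, so this is a ceiling.

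These points limit the likely size but do not close the gap. The plan would accept a withdrawal score that no text requires, which leaves the practice to each site, and it says nothing about women who end up without one.

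**Conclusion.** The concern holds as a gap in required data collection and in missing-data handling. It does not show that the comparison is confined to women who tolerated the device. Followed as written, the plan can omit women who withdrew for discomfort from a comparison of discomfort, and any resulting bias probably favours the study pessary. That direction rests on the assumption that unscored women had worse removals than scored women.

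The size cannot be determined from the documents. With a few such women the distortion is modest, as the k = 3 row shows. Removal pain is one secondary endpoint in an open-label feasibility study, with a reported p-value and no success criterion, so this is a cheap improvement of low to moderate priority.

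**What to change.** 1. **Protocol 6.0 (Visit 2 and Additional Visits) and 13.0:** record the 10 cm VAS whenever a practitioner removes the study pessary, including at withdrawal.
2. **Protocol 4.0 and 6.0:** reconcile the Week 5-7 time point for removal pain with the Visit 2 text, which names no VAS.
3. **SAP 11.3.1:** state that scores from Visit 2, unscheduled visits and withdrawal visits count as study-pessary removal scores.
4. **SAP 11.5:** report the number of fitted women without a study-pessary removal score, by withdrawal reason.
5. **SAP 11.5.3:** add a sensitivity analysis that includes device-related withdrawals without a score over a stated range of unfavourable values. The documents do not point to a particular penalty, so the range is for the sponsor to choose and justify in advance.

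The cost is one VAS line at a removal that already takes place, some SAP wording and one extra analysis. Items 4 and 5 remain possible after data collection has ended. The drawback is that withdrawal scores follow a shorter and varying wear time, so wear time should be tabulated beside them.

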## TITLE COLLAPSIBLE PESSARY FEASIBILITY TRIAL STATISTICAL ANALYSIS PLAN

**12.0 SUCCESS & EASE OF FITTING (SECONDARY)**

- 12.1 Endpoint
  - 12.1.1 Proportion of subjects successfully fit with the study pessary
  - 12.1.2 Number of study pessaries required to fit
- 12.2 Data collection method
  - 12.2.1 If subject is unable to be fit with a study pessary it will be recorded
  - 12.2.2 Size of each study pessary tried will be recorded
- 12.3 Analysis group
  - 12.3.1 All subjects who complete the study will be considered successfully fit.
  - 12.3.2 For those who do not complete the trial, if the study team indicates that the reason for withdrawal is failure to fit or failure to retain, the subject will be considered failed to fit. If the study team indicates that the reason for withdrawal is discomfort with the study pessary and multiple sizes of study pessary have been tried, the subject may be considered failed to fit. This may be indicated on the data collection form or in data safety monitoring meetings. All other subjects who received the study pessary and were not deemed fit failures will be considered successfully fit.
  - 12.3.3 For subjects who are successfully fit, each size tried will be considered a study pessary required to fit.
- 12.4 Data analysis plan
  - 12.4.1 A count of subjects who were successfully fit will be calculated.
  - 12.4.2 A count of subjects who failed to be fit will be calculated.
  - 12.4.3 A proportion of subjects successfully fit to total subjects (successfully fit + failed to fit) will be calculated.
  - 12.4.4 A count of total pessaries used will be calculated for each subject who completed.
  - 12.4.5 An average of number of pessaries required to successfully fit will be calculated.
- 12.5 Reportable outcomes
  - 12.5.1 The proportion of subjects successfully fit will be reported.
  - 12.5.2 The average pessaries required to fit will be reported.

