**CONFIDENTIAL**

## TITLE COLLAPSIBLE PESSARY FEASIBILITY TRIAL STATISTICAL ANALYSIS PLAN

## 6.0 PFDI-20 (PRIMARY)

- 6.1 Endpoint
  - 6.1.1 Pelvic Floor Distress Inventory-20 (PFDI-20) of study pessary compared to current pessary
- 6.2 Data collection method
  - 6.2.1 The PFDI-20 is a validated instrument to assess the presence and bother of symptoms that pelvic floor disorders have on health-related quality of life in women. It is a 20-item questionnaire and the short form of the 46 question PFDI. There are three subscales: Urinary Distress Inventory 6 (UDI-6), Colorectal-Anal Distress Inventory 8 (CRADI-8), and the Pelvic Organ Prolapse Distress Inventory 6 (POFDI-6). The overall score range is 0-300. The higher the score, the greater the perceived impact that pelvic floor dysfunction has on a patient's life.
- 6.3 Analysis group
  - 6.3.1 In the primary analysis, all subjects who complete visit 1 will be included in this intention to treat group. Subjects who drop out of the study prior to visit 1 are not included in this analytic group. Subjects who drop out and are included in the analytic group will be assigned the lower (i.e., worse) limit score of 18.3 for the study pessary.
  - 6.3.2 A secondary per protocol analysis will not include subjects who drop out because of failure to be fit.
- 6.4 Data analysis plan
  - 6.4.1 For each subject, the difference in score for the PFDI-20 for the current and the study pessary will be calculated.
- 6.5 Success criteria
  - 6.5.1 Wiegersma et al. determined the minimal important change (MIC) in the PFDI-20 to demonstrate a clinical effect to be 13.5-18.3 points in women choosing conservative management of their prolapse. Each analysis is a one-sample, equivalence design. We use 2, one-sided t-tests, each with alpha set at .05 to test the composite null hypothesis that the mean difference score ( $\mu_{reia-control}$ ) between baseline (current pessary) and study pessary on the PFDI-20, is greater than 18.3, the upper equivalence limit, or lower than -18.3, the lower equivalence limit:

H01:  $\mu_{reia-control} > 18.3$  and H02:  $\mu_{reia-control} < -18.3$ . The alternative hypothesis is thus: HA:  $-18.3 \leq \mu_{reia-control} \leq 18.3$

We reject the null hypothesis when the maximum p value across both t-tests is less than .05.

\* Printed copies are uncontrolled unless otherwise identified \*

Before using this document, consult Grand Avenue to confirm current version before use.

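### The fit proportion counts women who leave after fitting as successes by default, so as a Week 16 measure it can only err upward

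*SAP*

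**What the plan says.** Protocol 4.0 lists the endpoint under Other, with a post-treatment (Week 16) time frame, and describes it as "Proportion of subjects who were successfully fit with the study pessary".

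SAP 12.3 sorts women as follows:

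- Completers: "All subjects who complete the study will be considered successfully fit".
- Non-completers with a recorded fit or retention problem: "if the study team indicates that the reason for withdrawal is failure to fit or failure to retain, the subject will be considered failed to" be fitted.
- Non-completers with discomfort: if the reason is "discomfort with the study pessary and multiple sizes of study pessary have been tried, the subject may be considered failed to fit".
- Everyone else: "All other subjects who received the study pessary and were not deemed fit failures will be considered successfully fit".

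SAP 12.4.3 then gives the calculation: "A proportion of subjects successfully fit to total subjects (successfully fit + failed to fit) will be calculated". SAP 12.5.1 reports that proportion alone. No interval, bound or alternative count is planned.

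Protocol 13.0 lists inability to fit and repeated expulsion as one withdrawal reason. Adverse reaction and self-withdrawal are separate reasons, and one entry reads "The subject has a reaction that requires immediate removal of the study pessary". These do not match the SAP's failure categories, so they take the default. Loss to follow-up has no rule of its own and takes the default too.

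**The concern.** The SAP treats failure to retain as failure, so success must include keeping the pessary for some time. The protocol's Week 16 time frame points the same way. The default cuts across this in two ways.

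First, a woman lost or self-withdrawn after fitting has no later retention data, but the missing outcome is entered as success. If she would have gone on to expel the pessary, she counts as a failure when followed and as a success when lost.

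Second, a woman whose pessary was removed for a reaction is known not to be using it at Week 16, and she is also entered as success.

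The PFDI-20 analysis takes the opposite line on drop-outs after Visit 1: "Subjects who drop out and are included in the analytic group will be assigned the lower (i.e., worse) limit score of 18.3". That contrast is supporting evidence only, because a symptom score and a fit count need not share a rule.

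In a feasibility study of whether a new pessary can be fitted and kept in place, readers are likely to quote this proportion. As defined, it mixes early fitting with later retention, and the reader cannot tell how much of it was observed.

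**Working it through.** **Inputs**

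- At least 50 enrolled and at least 40 completing: Protocol 6.0, Methods. I use 50 and 40.
- Classification and denominator: SAP 12.3.1, 12.3.2 and 12.4.3.
- Neither document says how many losses fall in washout, or how many later losses would be recorded as fit failures. Both are assumptions, varied below.
- The plan states no expected fit proportion, so there is no planned figure to reproduce. The only related figure is 40/50 = 80% completing, on an enrolled basis.

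**Formulas**

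Let C = completers, w = women leaving in washout, f = recorded fit or retention failures, and o = other women who received the study pessary and left. Then C + w + f + o = 50.

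- SAP proportion = (C + o)/(C + o + f)
- Week 16 completion in the same denominator = C/(C + o + f)
- Gap = o/(C + o + f), which is never negative

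Women who leave in washout are in neither the numerator nor the denominator.

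**Results with C = 40**

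| w | f | o | SAP proportion | Week 16 completion | Gap (points) |
|---|---|---|---|---|---|
| 0 | 0 | 10 | 50/50 = 100% | 40/50 = 80% | 20 |
| 0 | 2 | 8 | 48/50 = 96% | 80% | 16 |
| 0 | 4 | 6 | 46/50 = 92% | 80% | 12 |
| 0 | 10 | 0 | 40/50 = 80% | 80% | 0 |
| 5 | 0 | 5 | 45/45 = 100% | 40/45 = 88.9% | 11.1 |
| 5 | 3 | 2 | 42/45 = 93.3% | 88.9% | 4.4 |
| 5 | 5 | 0 | 40/45 = 88.9% | 88.9% | 0 |
| 10 | 0 | 0 | 40/40 = 100% | 100% | 0 |

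The gap is measured against completion. The overstatement of true Week 16 retention is at most this large, because some lost women may still have been using the pessary.

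**Illustration of bounds**

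Suppose fitting is attempted in 50 women and 40 retain the pessary at Visit 3. Of the other 10, suppose 2 are recorded fit failures, 3 are removals for a reaction and 5 have unknown status. This split is assumed.

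- SAP figure: (40 + 3 + 5)/50 = 48/50 = 96% (exact 95% CI 86.3% to 99.5%)
- Retained, unknowns as failures: 40/50 = 80% (66.3% to 90.0%)
- Retained, unknowns as successes: (40 + 5)/50 = 45/50 = 90% (78.2% to 96.7%)

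Here the SAP figure exceeds even the upper bound by 3/50 = 6 points, which are the reaction removals.

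**The case against.** The strongest reply is that the endpoint is fit, not continued use. Week 16 may only be when the tally is made, and the protocol's description is in the past tense. Protocol 13.0 separates reactions and self-withdrawal from inability to fit, and the SAP follows that division. A woman who leaves at Week 10 for an unrelated reason, with a well-seated pessary, may fairly be called fit. Reactions are already counted under the primary safety endpoint.

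Much of this stands. A reader might infer that scoring a reaction removal or an unrelated loss as fit is a plain misclassification. The documents do not support that. It is a choice of estimand, and they do not define successful fit apart from the rule itself. What the reply does not remove is the mismatch: retention failures count when seen, the endpoint is dated to Week 16, and unseen failures count as successes.

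A reader might also infer that nothing is known about retention in women who are lost. Protocol 6.0 plans a call about pessary use just before Visit 2, which is due 1 to 3 weeks after Visit 1, and the call takes place even if the visit is then omitted. Only women lost before that contact have no retention information; for the rest, it is later retention that is unobserved.

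Finally, success is a default and not a certainty. The study team can attribute a self-withdrawal or a removal to failure to fit or retain, and it then counts as a failure.

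**Conclusion.** The concern holds as a limit on what the SAP 12.4.3 figure can mean. Read as a Week 16 result, it can be biased only upward, by at most the share of women who left after fitting without a recorded fit failure.

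A reader might take 100% against 80% as the expected distortion. The documents do not support that. The protocol's 40 of 50 is on an enrolled basis and includes washout withdrawals, which Protocol 13.0 anticipates. The 20-point gap needs all 10 losses to follow fitting and none to be recorded as a fit failure. With 5 losses after fitting the maximum is about 11 points. With none, or with all of them recorded as fit failures, it is zero.

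The endpoint is descriptive (Other in the protocol, secondary in the SAP), with no test or threshold. The effect is on a reported proportion, not on whether the study succeeds.

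**What to change.** - Keep the SAP 12.4.3 proportion and label it initial fitting success.
- Add to SAP 12.4 and 12.5 the proportion fitted and still retaining the study pessary at Visit 3, among all women in whom fitting was attempted.
- Report it twice, with women of unknown status as failures (lower bound) and as successes (upper bound), each with an exact 95% CI.
- Tabulate withdrawals for adverse reaction on a separate line, as not retained at Week 16.
- State what retention at Visit 3 means for self-managers, who remove and reinsert the pessary themselves.

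The lower bound should not become the sole headline. Counting every unknown as a failure would err in the other direction, so the two bounds belong together.

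The cost is some SAP wording and one extra tabulation from data already collected. The downside is a less favourable figure beside the headline.
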